## 14) Procedural success (must be present in all treated lesions and vessels):

Defined as A) angiographic core laboratory-assessed final (post-PCI) lesion angiographic diameter stenosis  $<30\%$  and target vessel TIMI III flow without any of the angiographic complications listed in 10(vi) above; plus B) the absence of site-assessed prolonged ST-segment elevation or depression ( $>30$  minutes), cardiac arrest or need for defibrillation or cardioversion or hypotension/heart failure requiring mechanical or intravenous hemodynamic support or intubation, or procedural death.

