**A second randomized target vessel:** Lesions requiring PCI in a 2nd target vessel (randomized lesions) may be treated during the index procedure (as long as no non-target vessels were treated during the same procedure) or staged >24 hours after the index procedure. However, all staged randomized procedures must be completed within 2 months (preferably 1 month) after the study procedure. The intent to stage such lesions should be declared at the time of randomization, but the decision to stage a randomized vessel which was not originally planned for staging may be modified in the case report form within 24 hours of the procedure to reflect changes in procedural strategy that may arise from the index PCI (e.g. treatment of the first vessel took longer than expected, or was complicated). The original treatment assignment must be used to guide all staged procedures. All staged procedures must be performed in a second target vessel – i.e. staged procedures cannot occur in a second lesion in the first target vessel treated during the index procedure. In no case, however, may a target vessel be randomized which was not declared as intended for study randomization prior to randomization. Note that for staged procedures, the assessments of troponin and/or CK-MB and a 12-lead ECG must be repeated within 8-16 hours prior to the staged procedure. If troponin and/or CK-MB readings are abnormal, they must be assessed either 8-16 hours after the last measurement or drawn from the sheath at the time of the procedure so a curve may be established for periprocedural MI adjudication. Note: patients with stable CAD may have the biomarker drawn from the sheath prior to any intervention, and the result does not need to be available prior to treatment.

[figure not shown]

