**Myocardial Infarction (Primary Protocol Definition)**

Periprocedural MI – Modified ARC-2 Definition

Periprocedural myocardial infarction occurring within 48 hours after all percutaneous coronary intervention (PCI) and coronary artery bypass grafting (CABG) procedures:

Absolute rise (from baseline to within 48 hours of procedure) in cardiac troponin of  $\geq 35x$  the 99th percentile URL (or  $\geq 35x$  ULN if URL is not available) or in the absence of cardiac troponin, rise in CK-MB to  $\geq 5x$  the 99th percentile URL (or  $\geq 5x$  ULN if URL is not available). Note, cardiac troponin assessments are preferentially used if available; otherwise CK-MB may be used.

In addition, 1 (or more) of the following measures of myocardial ischemia must be present post-procedure:

- New significant Q waves ( $\geq 40$  ms in duration and  $\geq 1$  mm deep in voltage in  $\geq 2$  contiguous leads) or equivalent
- Persistent flow-limiting angiographic complications in a major epicardial vessel or branch  $\geq 1.5$  mm in diameter present at the end of the PCI procedure (or during angiography performed to evaluate a post-CABG complication) as assessed at the angiographic core laboratory
- New substantial loss of viable myocardium on serial imaging

These assessments apply to patients: a) with baseline CK-MB or cardiac troponin levels  $\leq 1x$  the 99th percentile URL (or  $\leq 1x$  ULN if URL is not available); b) in whom the baseline biomarker is  $> 1x$  the 99th percentile URL (or  $> 1x$  ULN if URL is not available) and stable or falling; and c) with a single elevated

baseline draw who have a chronic coronary syndrome (CCS). In the latter two groups (patients in whom the baseline is elevated and stable or falling and CCS patients with a single elevated baseline draw), the post-procedural troponin (or CK-MB) must rise above the most recent baseline by an increment of the values above (i.e. for troponin  $\geq 35x$  the 99th percentile URL (or  $\geq 35x$  ULN if URL is not available) or in the absence of cardiac troponin, for CK-MB  $\geq 5x$  the 99th percentile URL (or  $\geq 5x$  ULN if URL is not available).

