- v. Post-PCI target vessel TIMI flow rate
 - vi. Angiographic complications – worst (anytime during the procedure) and final (post PCI and all imaging) - Angiographic dissection \geq NHLBI type B, perforations (Ellis classification), intra-procedural thrombotic events (including slow-flow, no-reflow, side branch closure, distal embolization, and intra-procedural stent thrombosis, as per the standard angiographic core laboratory definitions
- 11) Device Usage Endpoints (site reported; assessed per subject):
- i. Total stent length
 - ii. Total number of stents
 - iii. Maximal stent size
 - iv. Post dilatation (yes/no)
 - v. Total number of post-dilation balloons
 - vi. Maximal post-dilatation balloon size
 - vii. Maximal device size (stent or post-dilatation balloon)
 - viii. Maximum inflation pressure (atm.; stent or post-dilatation balloon)
- 12) Procedure time (first angiogram to guide catheter removal), fluoroscopy time, radiation exposure
- 13) Contrast use; contrast induced nephropathy (defined as serum creatinine rise $>25\%$ or absolute increase >0.5 mg/dL ($44.2\mu\text{mol/L}$)); need for renal replacement therapy
- 14) Procedural success (must be present in all treated lesions and vessels):
- Defined as A) angiographic core laboratory-assessed final (post-PCI) lesion angiographic diameter stenosis $<30\%$ and target vessel TIMI III flow without any of the angiographic complications listed in 10(vi) above; plus B) the absence of site-assessed prolonged ST-segment elevation or depression (>30 minutes), cardiac arrest or need for defibrillation or cardioversion or hypotension/heart failure requiring mechanical or intravenous hemodynamic support or intubation, or procedural death.

Abbott

Study Name: ILUMIEN IV

Statistical Analysis Plan

15) Procedural complications

Defined as A) angiographic core laboratory-assessed complications listed in 10(vi) above occurring anytime during the procedure; or B) site-assessed prolonged ST-segment elevation or depression (>30 minutes), cardiac arrest or need for defibrillation or cardioversion or hypotension/heart failure requiring mechanical or intravenous hemodynamic support or intubation, or procedural death.

16) OCT performance success (site reported) (OCT arm only):

OCT imaging performed both pre- and post-PCI

17) OCT imaging-related procedural complications (CEC adjudicated)

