Any procedural complications (e.g. angiographic dissection, perforation, thrombus, acute closure, etc.) requiring any active intervention (e.g. prolonged balloon inflations, additional stent implantation, pericardiocentesis, intubation, hemodynamic support or pressors, defibrillation or cardioversion) or death adjudicated by the CEC as definitely or likely attributable to the physical performance of OCT-imaging (e.g. passing the catheter through the vasculature or stent, or injecting contrast to clear the blood for imaging). For this definition, adverse events that arise due to changes in PCI strategy as the result of OCT findings are NOT considered OCT imaging-related procedural complications.

18) Additional interventions on the basis of the pre-PCI or post-stent OCT-imaging run that would not have been performed based on angiographic guidance alone (site reported; assessed per subject; OCT Arm Only):

- i. Use of larger balloon
- ii. Use of higher inflation pressures
- iii. Use of additional balloons
- iv. Use of additional stent(s)
- v. Performance of atherectomy
- vi. Other interventions

Reason(s) for additional interventions will be documented by the site (e.g. more calcium

Abbott

Study Name: ILUMIEN IV

Statistical Analysis Plan

than anticipated, greater stent under-expansion than appreciated angiographically, greater malapposition than appreciated angiographically, greater tissue protrusion or thrombus burden than appreciated angiographically, more severe edge dissection than appreciated angiographically, residual reference segment disease not appreciated angiographically, other)

Clinical outcomes at 30 days, 1 year, and 2 years (unless otherwise noted)

- 19) Target lesion failure (TLF; cardiac death, TV-MI or ischemia-driven target lesion revascularization (ID-TLR)
- 20) All-cause mortality
- 21) Cardiac and non-cardiac mortality
- 22) All MI
- 23) TV-MI, non-TV-MI and indeterminate vessel MI
- 24) Periprocedural MI and non-periprocedural MI
- 25) All revascularization
- 26) ID-revascularization and non-ID-revascularization
- 27) ID-TVR, ID-TLR, ID-non-TLR TVR, and ID-non-TVR
- 28) Definite, probable and definite/procedure stent thrombosis (ARC definition)
- 29) Relationship between immediate post-procedure OCT parameters (e.g. MSA, procedural success, malapposition, dissection, protrusion, etc.) and 2-year endpoint rates (e.g. TVF, TLF, all-cause mortality, cardiac death, TV-MI, all MI, ID-TLR, ID-TVR, and stent thrombosis)

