5.5.1 Analysis Method

Analyses of all secondary endpoints will be performed according to their randomized group regardless of the device attempted or implanted. All continuous secondary endpoints will be summarized descriptively by number of observations available, mean, standard deviation, median, minimum, maximum; categorical secondary endpoints will be summarized by, the number within each category and the percentage out of the total number of available observations for each randomized arm and overall subjects.

Procedural outcome and Additional Procedural Endpoints

For continuous endpoints, the summary statistics will be presented by randomized arm. Changes from baseline to follow-up, where applicable, will be assessed by ANCOVA, adjusting for the baseline measurement in each group, and least square means, differences thereof and 95% CI of the differences will be reported.

For categorical endpoints, the percentages of each category will be presented by randomized arm and compared using a 95% confidence interval for the difference.

Clinical outcomes

The endpoints will be summarized via Kaplan Meier estimates and a Kaplan-Meier plot. The following statistics will be reported at 1 year and 2 years: estimated event rates and its 95% confidence interval (CI), log-rank p-value, and hazard ratios with 95% Wald CI's obtained via Cox proportional hazards regression.

Abbott

Study Name: ILUMIEN IV

Statistical Analysis Plan

Relationship between immediate post-procedure OCT parameters and 2-year endpoint rates will be explored using univariate and Cox multiple regression.

Patient Reported Outcomes (PRO)

The end point of PRO will be summarized by randomized arm. [REDACTED]

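### Procedural success is listed as an OCT predictor of 2-year outcome, but it is not an OCT measure and by definition shares events with TVF, TLF, death and MI (minor point, exploratory analysis)

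*SAP*

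**What the plan says.** Item 29 of the secondary endpoints (SAP 5.5, and the same item in Protocol 1.6.3 and 5.3.3) is worded: "Relationship between immediate post-procedure OCT parameters (e.g. MSA, procedural success, malapposition, dissection, protrusion, etc.) and 2-year endpoint rates". The outcomes it names include TVF, TLF, all-cause mortality, cardiac death, TV-MI, all MI, ID-TLR, ID-TVR and stent thrombosis. The whole visible method in SAP 5.5.1 is: "Relationship between immediate post-procedure OCT parameters and 2-year endpoint rates will be explored using univariate and Cox multiple regression".

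Item 14 defines procedural success per subject, over all treated lesions and vessels. Its angiographic part requires a low residual stenosis and "target vessel TIMI III flow without any of the angiographic complications listed in 10(vi) above". Its clinical part requires that none of a list of site-assessed events occurred, a list that ends "hypotension/heart failure requiring mechanical or intravenous hemodynamic support or intubation, or procedural death".

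Two definitions in Protocol Appendix B matter here. Cardiac death includes all procedure-related deaths. Periprocedural MI requires a large biomarker rise within 48 hours plus, ordinarily, at least one of three ischemia criteria. One of these is "Persistent flow-limiting angiographic complications in a major epicardial vessel or branch", present at the end of PCI and assessed by the angiographic core laboratory.

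**The concern.** A regression of outcome on predictor is informative only if the predictor can be present without the outcome following by construction. A subject who dies in the procedure is a procedural failure by item 14. The same subject is a cardiac death by Appendix B, and so a TVF, TLF and mortality event. Where a persistent flow-limiting complication supplies the ischemia criterion for a target-vessel periprocedural MI, one core-laboratory finding contributes to both sides of the model.

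A reader of the final report would see procedural success in a list of OCT parameters, with a hazard ratio next to that for MSA. It could be taken as evidence that a good imaging result protects against events over two years. Part of that hazard ratio would only restate that some failures were defined by an outcome event.

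**Working it through.** **No figure to reproduce.** The documents give no sample size, power or rate for this regression. The check is a comparison of definitions, followed by a simulation on assumed inputs.

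**Step 1. Which predictors overlap with which outcomes.**

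| Predictor in item 29 | Shares a component with an outcome? |
|---|---|
| MSA, malapposition, OCT dissection, protrusion | No. These are core-laboratory OCT measurements |
| Procedural success | Yes. Procedural death is a component of cardiac death, all-cause death, TVF and TLF. A flow-limiting complication is one qualifying criterion for periprocedural MI, and so can enter TV-MI, all MI, TVF and TLF |

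ID-TLR and ID-TVR are repeat revascularizations. Stent thrombosis in Appendix B is timed from completion of PCI, with intraprocedural thrombosis defined separately. These outcomes are largely separate from procedural success.

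**Step 2. Hand calculation for one setting.** Take 2490 subjects (Protocol 7.1.2.2). Assume 10% procedural failure, 1% with an event that is both failure and TVF, and a 6% later TVF risk unrelated to failure.

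- Failures: 0.10 × 2490 = 249. Shared events: 0.01 × 2490 = 24.9.
- Later events among the remaining failures: 0.06 × (249 − 24.9) = 13.4.
- Risk in failures: (24.9 + 13.4) / 249 = 15.4%. Risk in non-failures: 6.0%. Ratio: 15.4 / 6.0 = 2.6.
- Without the shared events: 13.4 / 224.1 = 6.0% against 6.0%, ratio 1.0.

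The Cox estimate is somewhat higher (2.87 in the simulation below). The shared events come first and shrink the failure group against which later events are compared.

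**Step 3. Simulation with no true effect.** Single-covariate Cox model, 2490 subjects, 300 replicates per setting, two-sided 5% Wald test. Assumed ranges: procedural failure 5% and 10%; TVF on days 0-2 of 0.25%, 0.5% and 1%; half or all of these being failures by definition; later 2-year TVF 6% and 12%. Each row spans the four combinations of failure rate and later TVF.

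| Day 0-2 TVF | Share failures by definition | Median HR for failure | False rejection |
|---|---|---|---|
| 0.25% | half | 1.10-1.42 | 10-20% |
| 0.25% | all | 1.24-1.88 | 21-59% |
| 0.5% | half | 1.21-1.81 | 19-52% |
| 0.5% | all | 1.44-2.85 | 56-95% |
| 1% | half | 1.44-2.78 | 59-94% |
| 1% | all | 1.90-5.12 | 97-100% |
| Any of the above, day 0-2 events dropped | – | 0.95-1.06 | 2-6% |

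A separate run (7% later TVF, every shared event definitional, 0.25-1% shared) gave medians of 1.78-4.51 at 5% failure, 1.32-2.50 at 10% and 1.15-1.78 at 20%. The distortion shrinks as failure becomes more common.

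**Step 4. Staged vessels.** Follow-up starts at the end of the index procedure (Protocol 6.5.4), while "all staged randomized procedures must be completed within 2 months (preferably 1 month) after the study procedure". To test whether this matters, second-vessel values were entered as if known at time zero, again with no true effect. Assumptions: 5-20% of subjects staged, 1-3% with an event by day 60, 30-100% of pre-staging events preventing the measurement, and 10% total 2-year TVF. MSA had mean 5.8 mm² and SD about 2.07, the SD derived from quartiles 4.5 and 7.3 in Protocol Table 1.

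- Minimum MSA: HR 0.999-1.012 per mm², rejection 3-8%.
- Any procedural failure over index and staged PCI: HR 0.94-1.03, rejection 3-7%.
- A bare indicator that the second vessel was measured, which the SAP does not propose: HR 0.81-0.94, rejection 3-19%.

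Staging by itself adds at most a weak bias.

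**The case against.** The strongest reply is that little depends on this analysis. SAP 5.5 treats the secondary endpoints as descriptive, with no hypothesis tests, and 5.5.1 calls this one exploratory. It lies outside the testing hierarchy and the success criteria. Outcomes excluding periprocedural MI are already planned, in the major secondary endpoint and in items 24 and 30. All of this stands, and it limits the point to a minor one. It does not change what item 29 names as predictor and outcome.

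It is also fair that the overlap is partial. A complication without the biomarker rise is not an MI, and an MI that qualifies on Q waves or imaging loss is not a procedural failure by definition. The rows with half the early events definitional allow for this. At the lowest early rate they show only a small distortion.

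Three stronger readings are tempting, and the documents do not support them.

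- A reader might infer that the whole regression is circular, MSA included, and that the imaging primary endpoint is undermined. The OCT measurements share no component with the outcomes, and the Protocol (5.1 and 7.2) rests the choice of MSA on cited prior studies. An OCT-detected dissection followed by periprocedural MI is a real association.
- A reader might infer that staged measurements are placed before they exist and so create a strong predictor. SAP 5.5.1 does not say they enter at time zero, and Step 4 found almost no effect when they do.
- A reader might infer that rules for combining up to four lesions per subject, or for clustering, are missing. The MSA and TVF methods (SAP 5.2.3 and 5.3.2) are largely redacted and may contain them, so an omission cannot be shown.

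**Conclusion.** The point holds for procedural success alone. Item 29 labels it an OCT parameter although it is an angiographic and clinical composite, and it overlaps by definition with TVF, TLF, cardiac and all-cause death, TV-MI and all MI. The overlap follows from visible text and depends on no assumed rate.

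The size does depend on assumptions, because the documents disclose neither a procedural failure rate nor an early event rate. With 5-10% failure and 0.25-1% early events, at least half of them definitional, the apparent hazard ratio is about 1.1 to 5 where the true later effect is nil. It is about 1.0 after events in the periprocedural window are removed. The calculation also assumes that procedural deaths and periprocedural MIs are counted as events in this model, which is the plain reading of item 29.

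This is a minor correction to an exploratory analysis. No primary or major secondary conclusion is at risk.

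**What to change.** In item 29 and SAP 5.5.1, do one of the following:

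- remove procedural success from the OCT predictors; or
- keep it, described as an angiographic and clinical composite, and relate it only to events after the 48-hour periprocedural window, with no procedural death or periprocedural MI in the outcome.

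Leave the other predictors and outcomes as they are. A 48-hour cut for every predictor is not needed. It would discard early events, such as acute stent thrombosis, that malapposition, dissection or protrusion might genuinely predict.

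The cost is a change of wording and a little programming. Under the second option a few very early events leave this one exploratory model. They remain in the primary, major secondary and other descriptive analyses as already defined.

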5.6 Interim Analysis

5.7 Overall Sample Size

The sample size required for evaluation of the first primary endpoint of MSA is 1600 randomized subjects. [REDACTED]

5.8 Trial Success

The trial has two primary endpoints for MSA and TVF to compare the effectiveness of the OCT-guided PCI against the angiography-guided PCI. Both primary endpoints must be met in order to claim the study success.

5.9 Multiplicity Adjustment

ILUMIEN IV study is powered for testing the two hypotheses for the primary endpoints in a hierarchical order:

6.0 ADDITIONAL DATA

6.1 Baseline and Demographic Characteristics

Descriptive statistics of continuous variables will be presented by randomized arm and include sample size, mean median, standard deviation, minimum and maximum. For categorical variables, the number and percentage of subjects in each category will be presented by randomized arm. Baseline characteristics will be tabulated and compared between the two randomized arms by 95% confidence intervals of the difference.

6.2 Mortality

The number of deaths will be summarized by frequencies and percentages by randomized arm. Kaplan-Meier survival curves will be used to present deaths through longer term follow-up.

6.3 Adverse Events

Adverse events, serious adverse events and unanticipated adverse device effects (UADE) will be summarized from the time of index procedure in terms of number of events, the percentage of subjects with events.

6.4 Withdrawal

Withdrawals will be summarized for subjects who have withdrawn from the trial and will include days to withdrawal and reason for withdrawal.

6.5 Protocol Deviation

Protocol deviations will be summarized for subjects in whom a protocol deviation was reported. All protocol deviations will be reviewed by Abbott throughout the trial for identification of protocol deviations that are thought to be major.

Major protocol deviations include enrollment of a subject:

- whose informed consent was not obtained,
- who did not meet all of the inclusion or exclusion criteria,
- who had a procedure where the physician did not attempt OCT image acquisition in all

Abbott

Study Name: ILUMIEN IV

Statistical Analysis Plan

- target lesions prior to or after stent placement in the OCT arm,
- who had at least one target vessel not assessed with blinded post-PCI OCT in the angiography arm,
 - who had at least one target vessel receiving subsequent treatment following the intended blinded post-PCI OCT in the angiography arm,
 - who did not receive any post-PCI cardiac enzyme draws

All major protocol deviations will be summarized in the final study report.

6.6 Data for Roll-in Subjects

No hypotheses tests will be performed for the roll-in subjects. Data collected for the roll-in subjects will be summarized using descriptive statistics.

Abbott

Study Name: ILUMIEN IV

Statistical Analysis Plan

APPENDIX C: Pre-specified Powered Analysis of XIENCE in the In-Stent Restenosis (ISR) Population

Introduction

Abbott is evaluating the safety and effectiveness of treating in-stent restenosis (ISR) lesions with the XIENCE family of stents within the ILUMIEN IV trial. The trial enrolls patients undergoing planned XIENCE stent implantation during a clinically indicated PCI procedure who satisfy the eligibility criteria described in **Section 5.4** of the CIP. A pre-specified powered analysis of XIENCE is being conducted in randomized ILUMIEN IV subjects with ISR and is described below. The XIENCE ISR analysis is intended to support an indication expansion for treatment of ISR lesions with the XIENCE family of stents in the USA. The XIENCE ISR analysis will be conducted after the last enrolled patient reaches 2 years of follow-up.

The XIENCE ISR analysis is independent of the main ILUMIEN IV study objective outlined in **Section 1.1** of the CIP, which is to demonstrate the superiority of an OCT-guided stent implantation strategy as compared to an angiography-guided stent implantation strategy.

Objective

The objective of the XIENCE ISR analysis is to demonstrate the safety and effectiveness of XIENCE in the treatment of ISR lesions.

Analysis Population

[REDACTED]

Primary Endpoint

The primary endpoint for the XIENCE ISR analysis is target lesion failure (TLF_{ISR}). TLF_{ISR} is the event rate of the composite outcome of cardiac death, target vessel myocardial infarction (TV-MI) (per primary protocol definition in Appendix B), or ischemia-driven target lesion revascularization (ID-TLR), assessed at 1 year. For subjects with multiple target vessels, TLF_{ISR} in any vessel with at least one XIENCE stent implanted on an ISR target lesion constitutes an endpoint event. The primary endpoint TLF_{ISR} is assessed to evaluate the safety and effectiveness of XIENCE in ISR lesions. This endpoint must be met to demonstrate success for XIENCE in ISR lesions.

[REDACTED]

Abbott

Study Name: ILUMIEN IV

Statistical Analysis Plan

Statistical Considerations

The hypothesis for the XIENCE ISR analysis is as follows:

$$H_0: TLF_{ISR} \geq PG$$

$$H_a: TLF_{ISR} < PG$$

where PG (performance goal) equals 20%. The null hypothesis will be tested using a one-sided alpha of 2.5%.

Sample Size and Power

A sample size of 228 subjects will provide approximately 90% power to reject the null hypothesis

For the determination of binary event rates at time points such as 1 year, the denominators are defined as below based on the type of events.

- Death/MI/Revascularization (DMR) event

Subjects will be included in the analysis if they either had the DMR event by the analysis time point or they did not have the DMR event but had follow-up visit falling into the specific window. In other words, subjects will be included in a given analysis if it can be determined whether or not the subject would have had the DMR event by the time point.

- Special events such as Stent Thrombosis (ST)

Subjects will be included in the analysis if they either had the specific event (for example, for analysis on ST, only ST is considered) by the analysis time point or they did not have the event but had follow-up visit falling into the specific window. In other words, subjects will be included in a given analysis if it can be determined whether or not the subject would have had the specific event by the time point.

Abbott

Study Name: ILUMIEN IV

Statistical Analysis Plan

Subgroup Analyses

Subgroup analyses will be performed to examine the consistency of TLF_{ISR} across study subgroups for the following baseline variables:

- Gender: male vs. female
- Age (e.g., < 65 , ≥ 65)
- Race (all categories as well as white vs non-white)
- Ethnicity (Hispanic or Latino vs not Hispanic or Latino)
- ACS vs. non-ACS
- Diabetes vs. non-diabetes
- Long or multiple lesions (defined as intended total stent length in any single target vessel ≥ 28 mm) vs. short and single lesions
- Bifurcations: yes vs. no
- Angiographic severe calcification vs. non-calcification
- OCT-guided treatment vs. angiography-guided treatment
- Medication-treated diabetes mellitus vs. others

Poolability Analysis

Non-powered Secondary Endpoints

Non-powered secondary endpoints for the XIENCE ISR analysis to be assessed at 1 year are as follows:

1. Cardiac death $_{ISR}$

Statistical Analysis Plan

- 2. TV-MI_{ISR}
- 3. ID-TLR_{ISR}
- 4. Stent thrombosis_{ISR}
- 5. All-cause mortality_{ISR}

In addition, the following outcomes will be reported as sensitivity analyses at 1 year:

- 6. TV-MI_{ISR,SCAI} (periprocedural MI by SCAI definition and spontaneous MI by protocol definition)
- 7. Periprocedural MI_{ISR,SCAI} (by SCAI definition)
- 8. All MI_{ISR,SCAI} (periprocedural MI by SCAI definition and spontaneous MI by protocol definition)
- 9. TLF_{ISR,SCAI}; the composite of cardiac death, TV-MI_{ISR,SCAI} or ID-TLR

Note: In the XIENCE ISR analysis population, TV-MI_{ISR} and TV-MI_{ISR,SCAI} include MI events with confirmed target vessel involvement and indeterminate vessel MI events

The analysis procedures used for the analysis of the primary endpoint and secondary endpoints for the XIENCE ISR population will be the same as used for the endpoints for the full ILUMIEN IV population as described previously in this SAP.

The XIENCE ISR analysis is independent of the main ILUMIEN IV study objective; therefore, multiplicity adjustment of the primary endpoint TLF_{ISR} is not required.

Additional Analyses to Assess Impact of COVID-19

[REDACTED]

[REDACTED]

[REDACTED]

[REDACTED]

[REDACTED]

[REDACTED]

[REDACTED]

[REDACTED]

[REDACTED]

[REDACTED]

Sensitivity Analyses

Abbott

Study Name: ILUMIEN IV

Statistical Analysis Plan

[REDACTED]

Other Study Considerations

Unless otherwise noted in this appendix, study conduct for the ISR analysis population is the same as for the full ILUMIEN IV population. This consideration applies to risks and benefits, investigator records and reporting, adverse events, clinical data handling, monitoring, compliance, suspension or premature termination of the clinical investigation, ethical considerations, clinical investigation conclusion, publication policy and results reporting on clinicaltrials.gov website.

Abbott

Study Name: ILUMIEN IV

Statistical Analysis Plan

[Redacted text block]

[Redacted text block]

- [Redacted list item]
- [Redacted list item]
- [Redacted list item]
- [Redacted list item]

Abbott

Study Name: ILUMIEN IV

Statistical Analysis Plan

[Redacted content]

Abbott

Study Name: ILUMIEN IV

Statistical Analysis Plan

[Redacted]

[Redacted]

| | | |
|------------|------------|------------|
| [Redacted] | [Redacted] | [Redacted] |
| [Redacted] | [Redacted] | [Redacted] |
| [Redacted] | [Redacted] | [Redacted] |
| [Redacted] | [Redacted] | [Redacted] |
| [Redacted] | [Redacted] | [Redacted] |
| [Redacted] | [Redacted] | [Redacted] |
| [Redacted] | [Redacted] | [Redacted] |
| [Redacted] | [Redacted] | [Redacted] |
| [Redacted] | [Redacted] | [Redacted] |
| [Redacted] | [Redacted] | [Redacted] |
| [Redacted] | [Redacted] | [Redacted] |
| [Redacted] | [Redacted] | [Redacted] |
| [Redacted] | [Redacted] | [Redacted] |
| [Redacted] | [Redacted] | [Redacted] |
| [Redacted] | [Redacted] | [Redacted] |
| [Redacted] | [Redacted] | [Redacted] |
| [Redacted] | [Redacted] | [Redacted] |
| [Redacted] | [Redacted] | [Redacted] |
| [Redacted] | [Redacted] | [Redacted] |
| [Redacted] | [Redacted] | [Redacted] |

[Redacted]

[Redacted]

[Redacted]

Abbott

Study Name: ILUMIEN IV

Statistical Analysis Plan

[Redacted text block]

[Redacted text line]

| [Redacted] | [Redacted] | [Redacted] |
|------------|------------|------------|
| [Redacted] | [Redacted] | [Redacted] |
| [Redacted] | [Redacted] | [Redacted] |
| [Redacted] | [Redacted] | [Redacted] |
| [Redacted] | [Redacted] | [Redacted] |
| [Redacted] | [Redacted] | [Redacted] |
| [Redacted] | [Redacted] | [Redacted] |
| [Redacted] | [Redacted] | [Redacted] |
| [Redacted] | [Redacted] | [Redacted] |
| [Redacted] | [Redacted] | [Redacted] |
| [Redacted] | [Redacted] | [Redacted] |
| [Redacted] | [Redacted] | [Redacted] |
| [Redacted] | [Redacted] | [Redacted] |
| [Redacted] | [Redacted] | [Redacted] |
| [Redacted] | [Redacted] | [Redacted] |

[Redacted text line]

Abbott

Study Name: ILUMIEN IV

Statistical Analysis Plan

[Redacted text block]

[Redacted text line]

| | | |
|------------|------------|------------|
| [Redacted] | [Redacted] | [Redacted] |
| [Redacted] | [Redacted] | [Redacted] |
| [Redacted] | [Redacted] | [Redacted] |
| [Redacted] | [Redacted] | [Redacted] |
| [Redacted] | [Redacted] | [Redacted] |
| [Redacted] | [Redacted] | [Redacted] |
| [Redacted] | [Redacted] | [Redacted] |
| [Redacted] | [Redacted] | [Redacted] |
| [Redacted] | [Redacted] | [Redacted] |
| [Redacted] | [Redacted] | [Redacted] |

Abbott

Study Name: ILUMIEN IV

Statistical Analysis Plan

| | | |
|------------|------------|------------|
| [REDACTED] | [REDACTED] | [REDACTED] |
| [REDACTED] | [REDACTED] | [REDACTED] |
| [REDACTED] | [REDACTED] | [REDACTED] |
| [REDACTED] | [REDACTED] | [REDACTED] |
| [REDACTED] | [REDACTED] | [REDACTED] |
